9.2 Adverse Events

An Adverse Event is any untoward medical occurrence in a subject, regardless if there is a relationship between the adverse events and the study devices.

At each evaluation of the subject enrolled in a clinical investigation, the Investigator determines whether any adverse events (AE) have occurred, and determines their relationship to the study devices or procedure.

All adverse events, study device malfunctions and other product issues must be recorded in the medical records and entered into electronic Case Report Forms (eCRFs) within two weeks of awareness the AE occurred. Upon entry of an AE into the eCRF, designated members of the DePuy Synthes Mitek clinical team will receive an email alert describing the AE.

9.3 Serious Adverse Events

Serious Adverse Events (SAEs) are defined as any adverse event that:

1. Led to a death,
2. Led to a serious deterioration in the health of the subject that,
 - a. Resulted in life-threatening illness or injury,
 - b. Resulted in permanent impairment of a body structure or a body function,
 - c. Required hospitalization or prolongation of existing hospitalization
 - d. resulted in medical or surgical intervention to prevent permanent impairment to body structure or a body function,
3. Led to fetal distress, fetal death or a congenital abnormality or birth defect

A planned hospitalization and/or medical intervention for pre-existing conditions, or a procedure required by the protocol, without serious deterioration in health, is not considered to be a serious adverse event.

Investigator must submit to DePuy Synthes Mitek any SAEs occurring during the study as soon as possible, but within 72 hours, after being notified of the event and provide additional information if required by DePuy Synthes Mitek. All SAEs need to be followed until the event is resolved (with or without sequelae). The Medical Monitor of this study will decide if more follow-up information is needed (via electronic queries) in case the event is not resolved at study completion.

The Investigator notifies his/her EC/IRB of all SAEs occurred at his/her site (and any additional information as required by EC/IRB).

9.4 Unanticipated Adverse Device Effect (UADE)

An Unanticipated Adverse Device Effect (UADE) is defined as any serious adverse effect on health or safety or any life-threatening problem or death caused by, or associated with, a device, if that effect, problem, or death was not previously identified in nature, severity, or degree of incidence in the investigational plan or application (including a supplementary plan or application), or any other unanticipated serious problem associated with a device that relates to the rights, safety, or welfare of subjects.

Investigator must report to DePuy Synthes Mitek, either verbally or by eCRF entry, any UADE that occurs during the study within 72 hours after becoming aware of the event. Reporting by eCRF entry will trigger an email alert to DePuy Synthes Mitek. Investigator must provide additional information if required by DePuy Synthes Mitek to confirm that the event is a UADE. DePuy Synthes Mitek Sports Medicine will notify all participating Investigators and EC/IRBs of the UADE within 10 working days after confirmation of the event.

DePuy Synthes Mitek Sports Medicine will submit every year (unless otherwise indicated by the EC/IRB) to all participating Investigators an update of all study devices related, site reported and adjudicated SAEs. A letter summarizing the study status, enrollment figures, any safety concerns as well as any recommendation will accompany the updates.

9.5 Duration of Follow-up After Adverse Events

The Investigator should ensure that adequate medical care is provided to any subject for any adverse events, including clinically significant laboratory values, related to the study.

All adverse events related to the subject's participation in the study should be followed until the condition has resolved, or in the case of permanent impairment until the condition stabilizes and clinical outcome has been ascertained.

9.6 Reporting an Adverse Event

Adverse events are reported from the start time of the injection procedure until the subject's study participation has ended (i.e. completion of study or withdrawal of consent). All AEs must be followed until the AE has resolved, stabilized, or the study has been completed.

The Investigator will record the nature, severity, treatment and outcome of the AE, and will determine its relationship to the investigational products or any protocol mandated procedures involved in the clinical study.

The following categories of adverse event severity are to be used:

Mild	Awareness of sign or symptom that does not interfere with the subject's usual activity or is transient, resolved without treatment and with no sequelae,
Moderate	Interferes, but does not hinder, the subject's usual activity and may require treatment,
Severe	Symptom(s) causing severe discomfort and significant impact on the subject's usual activity and requires treatment or intervention.

The causal relationship should be rated as follows:

Unrelated	The event is definitely not associated with product application
Unlikely	The temporal sequence between product application and the event is such that the relationship is unlikely,
Possible	The temporal sequence between product application and the event is such that the relationship is not unlikely or the subject's condition or concomitant therapy could have caused the AE,
Probable	The temporal sequence is relevant or the event abates upon product application completion or the event cannot be reasonably explained by the patient's condition,
Related	The temporal sequence is relevant and the event abates upon product application completion or reappearance of the event on repeat product application (re-challenge).

Adverse events will be reported by the Investigator to DePuy Synthes Mitek Sports Medicine via the Adverse Events CRF.

10.0 EARLY DISCONTINUATION

10.1 Reasons for Early Discontinuation

Possible reasons for early discontinuation may include, but are not limited to the following:

- Withdrawal of consent: Subject decides to withdraw from the study. This decision must be an "independent decision" that is documented in the patient study files;
- Physician discretion: The Investigator may choose to withdraw a subject from the study if there are safety concerns;
- Adverse event: Adverse event or serious adverse event may not lead to subject discontinuation from the study. When the investigator decided to discontinue the subject, subject must be

followed until the adverse event resolves or until a stable clinical endpoint is reached;

- Death;
- Early study termination: DePuy Synthes Mitek Sports Medicine can decide to discontinue the study prematurely for various reasons, and/or
- Lost to follow-up: All subjects should be encouraged to return for all scheduled clinical follow-ups. If a subject is unable to return for mandatory clinical visits, 3 separate telephone calls or email messages should be made to attempt to bring the subject back into the clinic for follow-up visits. All attempts at contact should be documented in the source documents. If the subject does not respond to 3 telephone calls or emails, the Investigator must send a registered letter to the subject. If the subject does not respond to the registered letter and further contact is not made, then the subject will be considered to have missed the scheduled visit. If the aforementioned contact efforts are unsuccessful over two study intervals the subject will be considered lost to follow-up and an End of Study case report form must be completed.

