6.0 Study Design

This study is a prospective, multi-center, double-blinded, randomized, controlled, superiority study comparing intra-articular injections of MONOVISC High Molecular Weight Hyaluronan with intra-articular injections of physiologic saline. The study will take place at up to 40

investigational sites, primarily in the United States. Additional sites may be added in Canada and/or Europe. Subjects will be randomized through a 2:1 schema to receive either two (2) injections of 4 ml of MONOVISC, separated by 1 month (active treatment), or two (2) monthly injections of 4 ml of saline, separated by 1 month (control treatment).

Subjects will return for follow-up visits at 2, 4, 8, 16, and 26 weeks after the first injection.

The primary endpoint will be pain during walking (WOMAC A1) change from baseline at the 26 week time point.

An interim analysis of the primary endpoint will be conducted after 74 MONOVISC and 37 saline subjects have received both injections of MONOVISC or saline and completed their per protocol 26 week follow up visit. A stopping rule for futility will be implemented, such that the study will be terminated if the improvement of MONOVISC over saline (change from baseline) is less than 0.4 on a 10 point Numerical Rating Scale (NRS) in both the Per Protocol Analysis Set for the 26 week interval and the As Treated Analysis Set for the 26 week interval. If the improvement of MONOVISC over saline (change from baseline) is more than 0.4 NRS in either of these analysis sets, the study will continue to completion.

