10.3 Subject Early Discontinuation

Every subject should be encouraged to remain in the study until they have completed the protocol-required 26 week follow-up period. If the subject discontinues prematurely from the study, the reason for discontinuation must be documented in the source documents and site files, and submitted via CRF.

Subjects who have discontinued prematurely will be included in the analysis of results; however they will not be replaced.

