11.8 Analysis Sets

A detailed accounting of all enrolled Subjects will be documented with the following analysis sets.

Intent to Treat (ITT) Analysis Set

The Intent to Treat (ITT) Analysis Set consists of all subjects who are enrolled into the study. subjects in the ITT dataset but in whom treatment is not attempted with either MONOVISC or saline will be listed along with the reason for not being treated.

Safety Analysis Set

The Safety Analysis Set consists of all randomized subjects who are enrolled into the study, in whom treatment is attempted with either MONOVISC or saline. Subjects will be analyzed according to the treatment which is attempted.

As Treated (AT) Analysis Set for Each Study Defined Time Point

For each follow-up time point (the 2, 4, 8, 16 and 26 week visits), the As Treated (AT) Analysis Set (for the interval) will consist of all Safety Analysis Set subjects who have a follow-up visit within the interval in which WOMAC A1 pain data were collected. Reasons for not having WOMAC A1 pain follow-up in the interval will be documented (including deaths, withdrawals of consent, and Subjects who are past due for follow-up in the interval).

Modified Intent to Treat (MITT) Analysis Set (for Longitudinal Analysis)

All primary endpoint data from all As Treated Analysis Sets for the 2, 4, 8, 16 and 26 week visits will be combined into a dataset upon which longitudinal analysis for the primary endpoint can be conducted. In this MITT analysis set, primary endpoint data for the 26 week visit will be imputed with multiple imputation methodology.

Per Protocol (PP) Analysis Set for Each Study Defined Time Point

[figure not shown]
For each follow-up time point (the 2, 4, 8, 16 and 26 week visits), the Per Protocol (PP) Analysis Set (for the interval) will consist of As Treated Analysis Set subjects (for the interval), excluding protocol violations which are deemed to have possibly affected the scientific validity of the data. Note that some subjects may have data excluded from a particular Per Protocol Analysis Set for an interval (for example, if they used acetaminophen within 48 hours prior to a study visit), or from all Per Protocol Analysis Sets for all intervals (for example, if they failed an inclusion/exclusion criterion that is deemed to possibly affect the scientific validity of the data).

Per Protocol Analysis Set for Longitudinal Analysis

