11.9 Sample Size Justification

The sample size was determined based on the primary endpoint, which is a superiority comparison of WOMAC A1 pain change from baseline at 26 weeks for MONOVISC Subjects compared to Saline Subjects. Although it is planned to conduct the primary endpoint analysis with a longitudinal model, and to compare the WOMAC A1 pain change from baseline adjusted means at 26 weeks from this longitudinal model, the sample size was established based upon estimates for a t-test comparison of 26 week means for simplicity. Specifically, it is anticipated that the mean difference in WOMAC A1 pain change from baseline means will be at least 0.6 (where the mean for MONOVISC subjects is less than the mean for Saline Subjects), and that the standard deviation in WOMAC A1 pain change from baseline at 26 weeks will be approximately 2.2 in both groups. This standard deviation of 2.2 is consistent with published studies by Spitzer (2010) and Qvistgaard (2006); also, 2.2 is approximately $\frac{1}{4}$ of the maximum anticipated range of WOMAC A1 pain change from baseline, which would be an estimate of the standard deviation from data which are normally distributed. Using a two-tailed t-test and assuming a 2:1 randomization, the required sample size to yield 80% statistical power was estimated to be 318 MONOVISC and 159 Saline. With an anticipated attrition rate of 15%, the total study population was increased to be 560 patients (374 MONOVISC, 186 Saline). The sample size estimate was calculated with the following SAS code:

SAS Code for Power Estimation:
WOMAC A pain at 26 weeks

```
proc power;
  twosamplemeans
  meandiff= .6
  stddev=2.2
  groupweights=(2 1)
  power= .8
  alpha=0.05
  sides=2
  ntotal=.;
run;
```

The primary efficacy endpoint analysis will be conducted on the modified intent treat (MITT) Analysis Set with the handling of missing data at 26 weeks as described in Section 11.5 above. A supportive analysis will be conducted on the Per Protocol Analysis Set for Longitudinal Analysis.

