The primary efficacy endpoint analysis will be conducted on the MITT Analysis Set, which consists of all primary endpoint data on all As Treated (AT) subjects (regardless of whether or not there were protocol deviations associated with the data) for the 2, 4, 8, 16 and 26 week visits. In this MITT Analysis Set, missing primary endpoint data for the 26 Week visit will be imputed with multiple imputation methodology using SAS PROC MI with the regression method and a monotone missing data pattern.

No imputation of missing data will be performed for visits other than the 26 Week visit.

9 Primary and Secondary Endpoints

The primary and secondary endpoints are derived from the Western Ontario and McMaster Universities Arthritis Index (WOMAC), which is widely used in the evaluation of Hip and Knee Osteoarthritis. The WOMAC is available in over 65 languages and has been linguistically validated. It is a self-administered questionnaire consisting of 24 items divided into 3 subscales, A, B, and C: A) Pain (5 items), B) Stiffness (2 items), and C) Physical Function (17 items). The overall WOMAC score is determined by summing the scores across the 3 subscales and the score ranges include 0–24 (derived from the NRS scale). Higher scores on

the WOMAC indicate worse pain, stiffness, and functional limitations. Specific scoring details will be provided in the table shells document referenced in Section 15.

The WOMAC A is the pain subscale of the WOMAC questionnaire. Again, response options for individual questions are 0 through 10, where 0 indicates no pain and 10 indicates worst possible pain. The WOMAC A pain subscale scores ranges are 0-50 NRS.

WOMAC A1 is the first question of the WOMAC A and specifically addresses pain during walking. Response options are 0 through 10 NRS, where 0 indicates no pain and 10 indicates worst possible pain.

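### The lost-to-follow-up rule in Protocol 10.1 can close out an unreachable subject before the Week 26 window opens, with no Week 26 contact attempt then required

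*Protocol*

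**What the plan says.** Protocol section 6.0 sets the schedule: "Subjects will return for follow-up visits at 2, 4, 8, 16, and 26 weeks after the first injection". The primary endpoint belongs to the last of these visits (Protocol 11.6, SAP 9.1).

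For a subject who does not return, Protocol 10.1 prescribes three calls or emails and then a further step: "If the subject does not respond to 3 telephone calls or emails, the Investigator must send a registered letter to the subject". If that also fails, the visit counts as missed. The section continues: "If the aforementioned contact efforts are unsuccessful over two study intervals the subject will be considered lost to follow-up". Completing the End of Study form is then mandatory. The rule does not say whether the two intervals must be consecutive. It makes no exception for Week 26 and names no later attempt.

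Protocol 10.3 gives the retention aim: "Every subject should be encouraged to remain in the study until they have completed the protocol-required 26 week follow-up period". It adds that subjects who stop early are still to be analysed and are not replaced.

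On the analysis side, Protocol 11.8 builds the MITT set as follows: "All primary endpoint data from all As Treated Analysis Sets for the 2, 4, 8, 16 and 26 week visits will be combined". SAP section 8 says that "missing primary endpoint data for the 26 Week visit will be imputed with multiple imputation methodology", using the regression method under a monotone pattern.

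**The concern.** The rule treats all five follow-up intervals alike, but only Week 26 carries the primary endpoint. A subject who cannot be reached in two early intervals can be closed out while the primary visit is still weeks or months away. From then on nothing in the protocol asks the site to try again for that visit.

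What is at stake is primary data that might have been obtained. A multiply imputed value relies on the imputation model. The SAP's sensitivity analyses change the covariance structure and, under a condition, add covariates (SAP 13.4.1), and the per-protocol analysis does without imputation (Protocol 11.5). None of these examines a departure from missing at random. An observed score would remove that reliance for the subject concerned.

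**Working it through.** **1. The plan's own sample size.** Inputs from Protocol 11.9: the expected difference ("it is anticipated that the mean difference in WOMAC A1 pain change from baseline means will be at least 0.6"), SD 2.2, two-sided alpha 0.05, power 80%, allocation 2:1.

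Control n = (1 + 1/2) × (1.960 + 0.842)² × 2.2² / 0.6² = 1.5 × 7.85 × 13.44 ≈ 158.3, so 159 and 477 in total. This matches the plan. Exact t-test power at 318/159 is 0.8002. For 15% attrition, 477 / 0.85 = 561.2, rounded up to 562, against 560 stated, which is close enough. Conversely, 560 × 0.85 = 476 completers (317.9 / 158.1), with power 0.799. The plan therefore has no slack beyond 15%.

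**2. When close-out can happen.** Windows from Protocol 11.4: Week 2, Days 11 to 17; Week 4, 21 to 35; Week 8, 46 to 74; Week 16, 105 to 134; Week 26, 159 to 201. The gap is 159 minus the day the second failed window closes.

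| Consecutive failed intervals | Second window closes | Gap to Day 159 |
|---|---|---|
| 2 and 4 | Day 35 | 159 − 35 = 124 days |
| 4 and 8 | Day 74 | 159 − 74 = 85 days |
| 8 and 16 | Day 134 | 159 − 134 = 25 days |
| 16 and 26 | Day 201 | none; Week 26 was itself pursued |

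So 3 of the 4 consecutive pairs permit close-out before Week 26 is due. If the intervals need not be consecutive, 6 of the 10 possible pairs do (2+4, 2+8, 2+16, 4+8, 4+16, 8+16). Protocol 10.1 sets no waiting time for a reply to the registered letter, so a site that waits longer closes later. The 25-day gap is the one most easily used up.

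**3. What then happens to the Week 26 value.**

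- *At least one in-window visit.* The subject is in an As Treated set, hence in the MITT set, and the missing Week 26 value is imputed.
- *No in-window visit*, for example unreachable at weeks 2 and 4 and then closed out. The subject is in no As Treated set, hence not in the MITT set as Protocol 11.8 builds it. Nothing is imputed and the subject drops out of the primary analysis. This fits badly with the statement in 10.3 that early discontinuers are analysed.
- *Reached at Visit 7 after earlier gaps.* The 26-week As Treated set needs attempted treatment and an in-window WOMAC A1 visit, and does not need earlier visits. The mixed model in SAP 13.4.1 accepts subjects with gaps. The score enters the primary analysis as observed.

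**4. Scale.** The documents do not say how much of the 15% arises from this rule. As an assumed range, using completers only and the planned effect and SD, power is 0.821 with 10% of Week 26 data missing, 0.799 with 15%, 0.774 with 20% and 0.747 with 25%. Going from 15% to 10% means 560 × 0.05 = 28 more observed scores for a gain of 0.821 − 0.799 = 0.022, or about 0.022 / 28 ≈ 0.0008 per subject.

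**The case against.** The strongest reply is that the rule does not catch people who merely miss two visits. It applies after two full contact sequences have failed, which means six calls or emails (3 × 2) and two registered letters. Few such subjects are likely to answer a further attempt, and the power gained for each one who does is tiny. This stands, and it limits the size of the point. It does not explain why the one visit that carries the primary endpoint should be exempt from the sequence used for every other visit.

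A second reply is that subjects recovered at Week 26 after earlier gaps do not fit the monotone pattern in SAP section 8. Such gaps already arise under the plan, since one unreachable interval is only a missed visit and the subject may return. A Visit 7 attempt adds no new kind of problem.

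Several stronger readings are tempting, and the documents do not support them:

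- *Week 26 is never sought.* Section 10.1 is silent after close-out and does not forbid contact. If Week 26 is one of the two failed intervals, it was pursued.
- *The endpoint is always imputed instead.* A subject with no in-window visit is omitted.
- *Sections 10.1 and 10.3 contradict each other.* Section 10.3 asks for encouragement and then provides for early discontinuation. The two can coexist, though uneasily.
- *Adverse event reporting is cut short.* Protocol 9.6 ends participation at study completion or withdrawal of consent and does not list loss to follow-up. For an unreachable subject the gap comes from non-contact, not from the form.

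**Conclusion.** The point holds in a limited form. The rule can end follow-up before the only primary time point is due, and the protocol then requires no attempt to obtain it, although the value would be usable. This follows from the wording of 10.1 and the windows in 11.4, with the close of the second window taken as the close-out date.

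The benefit of changing it is probably small. It cannot be quantified from the documents, which give neither the share of attrition due to this rule nor the chance that such a subject would respond later. No bias or difference between arms is shown. The case for acting is that the change is cheap and serves the plan's own retention aim. It is a worthwhile improvement and not a defect that threatens the trial.

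**What to change.** Change the last sentence of the lost-to-follow-up item in Protocol 10.1 so that:

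- failed contact at any visit before Week 26 counts as a missed visit only;
- lost-to-follow-up status is assigned, and the End of Study form completed, only after the same contact sequence has been repeated for Visit 7 and the Week 26 window has closed (Day 201).

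Limit the change to this path. Withdrawal of consent, physician discretion, adverse events, death and early study termination remain as 10.1 has them. No hypothesis, model or sample size changes.

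The cost is one further round of calls or emails and a letter for each affected subject. Records stay open longer: up to 201 − 35 = 166 days after weeks 2 and 4, 201 − 74 = 127 days after weeks 4 and 8, or 201 − 134 = 67 days after weeks 8 and 16. A protocol amendment is also needed, with the approvals described in Protocol 12.7 and 14.4.
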